fMRI data analysis MRI images were preprocessed and analyzed through SPM8 (SPM8; Wellcome Trust Centre for Neuroimaging). Slice timing correction was performed for functional volumes. Functional volumes were realigned to the first volume in the experiment to correct for head motion, co-registered with the high-resolution sagittal images. The structural images were spatially normalized to a standard MNI template using the voxel-based morphometry toolbox (VBM8 <http://dbm.neuro.uni-jena.de/vbm>) and DARTEL high-dimensional warping and resampled to a 3x3x3 mm voxel size. Estimated deformation fields from warping were applied to normalize images to MNI space, and smoothed using a 5-mm FWHM Gaussian kernel. Motion scrubbing (removal of volumes) was performed based on a framewise displacement threshold of 0.3. The time course data for each voxel was band-pass filtered (0.01 to 0.10 Hz band) to capture the low-frequency spontaneous BOLD oscillations in resting state signals.

Task analysis

For the spatial navigation task, preprocessed MRI data were analyzed with the general linear model framework in SPM8. Two block regressors were modeled: allocentric and egocentric. The onsets and durations of blocks were convolved with a canonical hemodynamic response function (HRF) to create the block regressors, in addition to covariates of six image realignment parameters to reduce movement induced artifacts. In the first-level analysis for each participant, the parameter estimates of block regressors were computed at each voxel. Appropriate linear contrasts were applied to the parameter estimates to produce contrast images and statistical parametric maps (SPM t map). To evaluate activations associated with task, session, and group effects, we've

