We have further applied a 'data-driven' approach based on Graph Theory to analyze the functional connectivity network before and after the intervention. We've used Power's 264 anatomical coordinates to segment the brain into 264 ROIs. We included additional medial temporal and subcortical ROIs. Each ROI was defined as a 5 mm sphere centered around these coordinates. A binary grey matter mask was created through the segmentation procedure in VBM8 and the threshold probability of 0.6 (as suggested by Zalesky et. al.) was used to overlay on the normalized resting state images. The average time course signal of the grey matter voxels in each ROI was measured. Pearson's correlation between the signal time course of all possible pairs of ROIs was conducted. Correlation weights that failed the false discovery rate (FDR) threshold at $p < 0.05$ were discarded. Graph parameters, including total functional connections, network strength, and network cost were calculated.

Within each group (HC and MCI), we will use the active > sham contrast to identify regions that differ as a result of HD-tDCS. Correlations between behavioral performance (e.g., accuracy in CM) and BOLD signal will also be calculated to determine whether the altered BOLD signal is behaviorally meaningful. Because we expect functional reorganization throughout the brain within both groups as a result of HD-tDCS, we intend to use connectivity analyses to examine changes in the connectivity between the parietal cortex and the remainder of the brain.

Exploratory between group analysis will use two primary contrasts. 1) HC sham > MCI sham – which will identify disease-related differences in activation between the groups; 2) HC active > MCI active – which will examine whether the tDCS-related changes are greater in one group than the other. Taken together, these contrasts will also clarify whether tDCS restores functioning in brain regions involved in "normal" (i.e., age appropriate) navigation or whether it allows MCI patients to recruit alternative brain regions in a compensatory manner.

Additional analyses will be performed as necessary in order to fully characterize the nature of tDCS-related changes.

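### The exploratory HC–MCI activation contrasts carry no grey-matter term, so part of any HC > MCI gap could reflect tissue amount rather than function; add a sensitivity analysis and judge restoration on the active–sham change.

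*Combined protocol and SAP*

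**What the plan says.** All references are to the combined protocol and SAP.

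- **Between-group contrasts** (paragraph on group comparisons near the end of Statistical Design): "Exploratory between group analysis will use two primary contrasts". The first is HC sham > MCI sham, "which will identify disease-related differences in activation between the groups". The second is HC active > MCI active, "which will examine whether the tDCS-related changes are greater in one group than the other". The pair is then meant to show "whether tDCS restores functioning in brain regions involved in" age-appropriate navigation, or whether patients recruit other regions instead.
- **Task analysis**: the first-level model has allocentric and egocentric block regressors, "in addition to covariates of six image realignment parameters to reduce movement induced artifacts". The second level is a mixed ANOVA on task, session and group. No tissue term is named at either level, or in the ANOVA on extracted betas. The ROIs are hippocampus, superior parietal lobule and caudate, taken from a template atlas.
- **Grey matter**: VBM8 and DARTEL are used for normalisation. In the resting-state graph analysis, "A binary grey matter mask was created through the segmentation procedure in VBM8", with a probability threshold of 0.6, and only grey-matter voxels are averaged in each ROI. No matching step is described for the task contrasts.
- **Covariates**: the sentence allowing confounders as covariates belongs to the behavioural ANOVA and names none. The closing sentence on further analyses does not commit to a tissue adjustment.

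**The concern.** A template ROI covers the same standard-space volume in everyone. If that volume holds less grey matter in one group, the average BOLD estimate can be lower there even when the response per unit of tissue is the same. The Objectives describe MCI as a precursor of Alzheimer's-type dementia and the hippocampus is a named ROI, so the question is a natural one.

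A tissue difference would be present in both sessions, and a 20-minute stimulation would not remove it. It would therefore tend to produce HC > MCI under sham and again under active. Read as the plan proposes, that pattern looks like a disease-related activation deficit that tDCS failed to restore. Specific Aim 2 treats restoration versus compensation as an important question, although the between-group analysis itself is labelled exploratory.

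**Working it through.** The plan gives no effect size, SD or power figure for these contrasts, so there is no figure of its own to reproduce. What follows is an illustration.

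**Inputs from the documents.** Enrolment is up to 60. Whole-brain maps are thresholded at p<.01 to .001 uncorrected, ROIs at small-volume FWE p<.05, and extracted betas of surviving activations at p<.05 (Task analysis).

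**Assumptions, not in the documents.** A 30/30 split with everyone scanned; relative grey-matter loss L in MCI of 10–20%; BOLD estimate proportional to grey matter; positive mean response; between-person CV of 30–80%; equal response per unit of tissue in both groups.

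**Step 1: spurious effect size.** Group shift = L × mean response and SD = CV × mean response, so d = L / CV. The smallest value is 0.10/0.80 = 0.125, a middle value is 0.20/0.50 = 0.40, and the largest is 0.20/0.30 = 0.67.

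**Step 2: chance of declaring HC > MCI.** One-sided two-sample t-test on one pre-set region, with noncentrality d × √(n/2):

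| n per group | d | p<.05 | p<.01 | p<.001 |
|---|---|---|---|---|
| 30 | 0.125 | 12% | 3% | 0.4% |
| 30 | 0.40 | 45% | 21% | 5% |
| 30 | 0.67 | 82% | 58% | 27% |
| 20 | 0.125 | 10% | 3% | 0.3% |
| 20 | 0.40 | 34% | 13% | 3% |
| 20 | 0.67 | 66% | 38% | 13% |

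The rows for 20 matter because the plan gives no HC:MCI split and enrols some people who cannot be scanned.

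**Step 3: dependence on the contrast.** The plan does not say which task contrast feeds the group comparison. For allocentric minus egocentric, the shift is L × (mean allocentric − mean egocentric), which is near zero where the two conditions respond alike. For a negative mean response the bias reverses, to MCI > HC.

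**Step 4: the restoration reading.** A simulation (4,000 runs per scenario, 30 per group, one-sided .05) assumed an HC grey-matter fraction of 0.70, a within-group SD of 8% of that, CV 30–50%, and a tDCS gain of 0.2 (SD 0.4), equal in both groups per unit of tissue.

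| Tissue deficit | Sham and active contrasts both falsely positive | Group-by-session false positive |
|---|---|---|
| 0% | 2–3% | about 5% |
| 10% | 12–17% | 7–8% |
| 20% | 37–61% | 10–11% |

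The change score is much less affected because tissue scales only the gain (0.2), not the whole response (1.0). With the grey-matter value as a covariate, each separate contrast returned to about 5% and both together to 1.4–2.6%.

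**Step 5: cost of adjusting.** With the same inputs and a 20% deficit, grey matter separates the groups by 0.20/0.08 = 2.5 SD. The variance of the adjusted group effect rises by 1 + 2.5²/4 = 2.56. For a true d of 0.8 with 30 per group at one-sided .05, power falls from 92% to 61%.

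**The case against.** The premise is assumed. The documents contain no grey-matter figure for either group and never say that the MCI participants have less tissue. Tissue loss, proportionality and CV are all outside inputs, and the resulting range is too wide to predict what this trial would see. That stands: the calculation shows a possibility, not an expected bias.

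The p<.05 column is the most lenient. The plan's maps use stricter thresholds, and its p<.05 ANOVA applies only to betas that have already survived. Direction and size also depend on a contrast that is not specified. Both points stand, and are why the range is given by threshold.

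The restoration misreading is not only a tissue problem. HC active > MCI active does not measure change, so any standing group difference, including a genuine functional one, produces the same pattern. A tissue covariate does not cure that. This also stands, and it changes the fix.

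Adjustment can do harm where tissue loss lies on the path from disease to activation. A reader might infer that only a gap surviving adjustment should count as an activation deficit. Nothing in the documents supports such a rule, and step 5 shows it could hide real deficits.

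Finally, the label for the first contrast is not strictly false if atrophy contributes, since atrophy may itself be disease-related. But the label speaks of activation, and the plan goes on to use it for functioning, so the distinction still matters.

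**Conclusion.** The omission is real and its consequence is limited. No grey-matter term enters the task model, the beta ANOVA or the two HC–MCI contrasts, while the plan restricts its resting-state graph analysis to grey-matter voxels. If MCI participants have less tissue in a positively responding region, part of an HC > MCI gap could be structural and would appear in both sessions. The single-test false-positive chance is 12–82%, 3–58% or 0.4–27% at one-sided p<.05, .01 or .001. These ranges hold only under the stated assumptions with 30 scanned per group.

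Three stronger readings are not supported:

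- That the contrasts are biased in this trial: the documents give no tissue data.
- That the within-group active > sham contrasts are compromised: each person is their own control, so tissue amount can scale a change but not create one.
- That a grey-matter value is certainly on file for every participant: the text mentions a mask and VBM8/DARTEL processing, from which individual segmentation is a fair inference but not a statement.

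This is a worthwhile improvement to an exploratory analysis and does not touch the primary behavioural analysis.

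**What to change.** 1. Report HC sham > MCI sham and HC active > MCI active with and without each participant's VBM8 grey-matter value (voxelwise map or ROI mean) as a covariate, labelled a sensitivity analysis.
2. Describe a difference that disappears after adjustment as possibly tissue-related, not as an established activation deficit. Do not make the adjusted result a condition for reporting a difference.
3. Judge restoration on the active–sham change, using the group-by-session term of the mixed ANOVA already planned, and not on HC active > MCI active alone.
4. State which task contrast (each condition alone, or allocentric minus egocentric) enters the group comparison.

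Cost: one more second-level run per contrast on existing images, after confirming that segmentations exist for every scanned participant. No new data or visits are needed. The downside is over-adjustment and lower power where tissue loss and function fall together, which is why both versions are reported.

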Participants: We will enroll up to 60 older adults (age 50+), who are right handed and MRI compatible, from the VA Ann Arbor Healthcare System, the University of Michigan Alzheimer’s Disease Center (MADC), and the surrounding community. Enrollment is open to participants regardless of race, gender, or social status.

Inclusion criteria: Patients will receive a diagnosis of MCI based on the Albert et al. (2011) criteria. Specifically, patients will **1)** report a subjective decline in memory (report can also be provided by an informant), **2)** demonstrate objective impairment in memory (based on Neuropsychological testing), and **3)** remain independent in activities of daily living. All patients will be stable on nootropic medications for at least 1-2 months prior to study initiation.

By definition, healthy controls (HC) will be free of objective memory test impairment (i.e., all scores within normal limits on the standardized testing protocol below).

Exclusion criteria: A history of **1)** contributory other neurological (e.g., epilepsy, moderate - severe traumatic brain injury) or medical conditions that are known to affect cognitive functioning; **2)** significant psychiatric conditions (e.g., moderate - severe depression, bipolar disorder, schizophrenia); **3)** sensory impairments that limit the ability to take part in the study; **4)** a significant history or current use of alcohol or drug abuse/dependence. Participants will also be screened to ensure MRI compatibility (assessed using the guidelines set forth by the American College of Radiology); some of the criteria for which are also reasons for excluding someone from tDCS (e.g., metallic or electronic implants). Eligible participants who cannot undergo MRI will be enrolled in the study and will complete only the stimulation and behavioral portions of the study. We have successfully used this same approach in our previous RCTs.

Recruitment: Participants will be recruited from both the VA Ann Arbor Healthcare system and the University of Michigan Alzheimer’s Disease Center. The primary recruitment source of MCI patients at the VA will be the Neuropsychology Clinic while HC will be recruited from the general VA community via postings/flyers in approved areas. The primary recruitment site for non-Veterans will be the University of Michigan Alzheimer’s

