Eligible participants will undergo 2 sessions within a 2-week period of time. Some degree of flexibility is necessary with these visits in order to accommodate both patient and MRI availability.

Once determined to be eligible, participants will be randomized to one of two groups within their respective diagnostic groups. The first group will receive active HD-tDCS during session 1 and then sham HD-tDCS during session 2. The second group will receive the opposite order.

Participants will first receive 20 minutes of HD-tDCS at 2mA or sham as appropriate to the assigned condition. Participant specific codes are entered into the Soterix Medical Inc Clinical Trial unit thereby ensuring participants and study staff are blinded to stimulation condition. Stimulation will be performed using a Soterix Medical Inc. tDCS unit (Clinical Trial system with attached 4x1 HD stimulation unit) within a quiet room. The unit automatically discontinues stimulation after the specified time has elapsed (here 20 minutes). The patient will

complete a brief questionnaire about the nature and severity of any side effects (see tDCS Safety below) as well as whether they believe they received active or sham stimulation.

The active tDCS protocol will provide an initial ramp-up period in which the electrical current is gradually increased, followed by 20 minutes of stimulation at 2mA, and finally a ramp down period during which the electrical current is gradually removed.

The sham tDCS group will receive a ramp-up period to 2mA followed immediately by ramp down period. This is repeated at the end of the session.

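### The exploratory HC sham > MCI sham contrast may mix disease with nootropic drug effects, so it cannot by itself be called disease-related

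*Combined protocol and SAP*

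**What the plan says.** All references are to the combined protocol and SAP.

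- **Inclusion criteria (Participants).** For MCI patients: "All patients will be stable on nootropic medications for at least 1-2 months prior to study initiation". For controls, the definition is that "healthy controls (HC) will be free of objective memory test impairment". Nootropic use in controls is neither excluded nor mentioned.
- **Study Procedures.** Only stimulation order is randomised: "participants will be randomized to one of two groups within their respective diagnostic groups".
- **Task analysis.** The first-level model has the two task regressors, "in addition to covariates of six image realignment parameters to reduce movement induced artifacts". The second-level mixed ANOVA is described as "To evaluate activations associated with task, session, and group effects". No medication term is named there or under Resting state analysis.
- **Between-group paragraph near the end of the statistical text.** "Exploratory between group analysis will use two primary contrasts". The first, HC sham > MCI sham, is one "which will identify disease-related differences in activation between the groups". The second, HC active > MCI active, is one "which will examine whether the tDCS-related changes are greater in one group than the other". The two are then read together to judge whether tDCS restores normal navigation activity or works through compensation.
- **Specific Aim 2** treats restoration versus compensation as a critical question, to be answered by comparing BOLD signal change between the groups.

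**The concern.** A stability rule holds a patient's medication constant from one session to the next, which protects comparisons within a person. It does nothing to balance medication between patients and controls. If more MCI patients than controls take nootropics, and if these drugs alter BOLD signal, the sham contrast contains a drug component that the plan would report as disease. A drug that moves patients towards the control level would instead hide a disease difference. Either error would affect which regions are taken to show normal activity, and that judgement feeds the restorative-versus-compensatory interpretation.

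**Working it through.** The plan gives no sample size, effect size or medicated share for this contrast, so it has no figure to reproduce. The check has two parts.

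**1. Where the drug shift goes**

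Let D be the HC minus MCI difference without any drug, T the HC minus MCI difference in tDCS effect, and m the shift of the MCI mean relative to HC caused by unequal drug use:

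m = (medicated share in MCI − medicated share in HC) × drug effect.

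For a stable drug whose effect is the same under sham and active stimulation:

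- Contrast 1, HC sham − MCI sham = D − m
- Contrast 2, HC active − MCI active = D + T − m
- Contrast 2 − contrast 1 = T

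The shift m is in each contrast as written and drops out of their difference. If the shift is m_s under sham and m_a under active, the difference becomes T − (m_a − m_s), so bias in the change requires a drug-by-stimulation interaction. Contrast 2 alone also carries D, so even without any drug it does not isolate a difference in tDCS-related change. Active minus sham within a person involves no comparison of medicated with unmedicated people.

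**2. Possible size in contrast 1**

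From the documents: enrolment of up to 60; people who cannot have MRI are still enrolled but not scanned; extracted beta values are tested at p < .05.

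Assumed, because the documents are silent: an even split; 20 or 30 scanned per group (30 is the upper bound for an even split of 60); no nootropic use in HC; no true disease effect (D = 0); and these combinations of MCI medicated share and drug effect:

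- 50% × 0.3 SD = 0.15 SD
- 50% × 0.5 SD = 0.25 SD
- 70% × 0.5 SD = 0.35 SD

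Test: two-sided two-sample t at 5%, noncentrality = bias × √(n/2), df = 2n − 2. For example, with n = 30 and bias 0.25, noncentrality = 0.25 × √15 = 0.968.

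| Bias (SD) | Rejection rate, n = 30 per group | Rejection rate, n = 20 per group |
|---|---|---|
| 0.15 | 8.8% | 7.5% |
| 0.25 | 15.9% | 12.0% |
| 0.35 | 26.6% | 19.0% |

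If no patient is medicated, or the shares are equal in the two groups, m = 0 and the rate is 5%.

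**3. Precision of an unmedicated comparison**

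With 30 HC and 15 unmedicated MCI (half of 30 medicated): SE = √(1/30 + 1/15) = 0.316 SD, and the 95% half-width = 2.017 × 0.316 = 0.64 SD. That is wider than any bias in the table.

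**The case against.** **The plan may already allow for this.** Statistical Design permits confounders as covariates, and the last sentence of the analysis text allows further analyses. The covariate option is discretionary, names no factor and belongs to the behavioural ANOVA. The other sentence concerns tDCS-related changes. Neither covers medication in the fMRI group contrasts.

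**The contrast is exploratory.** This stands and limits the weight of the point. The wording still asserts that the contrast will identify disease-related differences, and Aim 2 calls the question it feeds critical.

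**The confounding is inferred.** This also stands. A reader might infer that controls take no nootropics and that the contrast therefore does mix drug with disease. The documents do not say so: they are silent on controls' use, give no medicated share among patients, and state no drug effect on BOLD. They support possible confounding only.

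**The error need not reach the restorative-versus-compensatory conclusion.** A reader might infer that it carries over in full. An additive stable shift cancels from the between-group difference in change, which is how Aim 2 frames the question. What remains is the shift in each of the two contrasts as written.

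**The illustrated test is not the plan's ROI test.** This is correct. The ROIs are small-volume corrected at voxel-wise FWE, whereas the table uses a single 5% test. It shows scale only.

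**Conclusion.** The concern holds in limited form. Patients may be medicated, controls' use is not addressed, diagnosis is not randomised and no fMRI model includes medication. HC sham > MCI sham is therefore a comparison of controls with MCI patients as treated, and the plan cannot attribute a difference to disease from that contrast alone. HC active > MCI active shares the problem as written.

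The size in this trial cannot be found from the documents. The range of about 7.5% to 27% rests entirely on the assumed 20 to 30 scanned per group and 0.15 to 0.35 SD of bias. A shift in the other direction could mask a real difference.

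A reader might go further and infer that the tDCS effect itself is confounded by medication. The documents do not support that: the within-person active > sham contrasts are unaffected by a drug held constant across both sessions.

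**What to change.** 1. Code nootropic use (yes/no) at session 1 for every participant in both groups, and report it by group.
2. Describe contrast 1 as a difference between HC and MCI as treated, in place of disease-related.
3. If numbers allow, repeat both between-group contrasts as a sensitivity analysis in participants not taking nootropics. Report estimates and 95% intervals with no pass/fail rule.
4. Base any statement that tDCS-related change differs by group on the group-by-stimulation contrast (active minus sham, HC versus MCI).

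**Cost.** SAP wording, one medication variable and extra runs on existing data. Patients' status must already be known to apply the stability criterion; controls' status may have to be asked. No added visits or scans are needed.

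**Downside.** The unmedicated comparison is imprecise (half-width about 0.64 SD with 30 HC and 15 MCI) and may select milder patients, exchanging drug confounding for severity confounding. Read literally, the stability criterion could mean that every patient is medicated. In that case no unmedicated MCI comparison exists, and of the steps aimed at the drug question only the wording change applies.

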**Title: Enhancing Spatial Navigation using Non-Invasive Brain Stimulation
NCT01958437**

PI: [name], ABPP/CN

Objectives: Remembering how to travel from one location to another is critical in everyday life, yet this vital ability declines with normal aging and can be further affected by conditions that disproportionately affect older adults, such as progressive dementia. Human and animal research has shown that two distinct memory systems interact during navigation. The first, referred to as allocentric navigation, is flexible and uses spatial knowledge of key features or landmarks to develop and use a mental map of the environment. This approach involves brain regions that are critical for new learning and memory but that decline with age. The second, referred to as egocentric navigation, is inflexible and relies on “habit” memories that link specific features with specific directions. This approach relies on brain regions that are critical for “automatic” responses and that are relatively unaffected by age.

The main problem is that allocentric navigation declines with age and is accompanied by increased dependence on egocentric navigation. This change increases the risk of becoming disoriented or “lost” when traveling in unfamiliar areas or even when traveling new routes in familiar areas. Therefore, **the main goal** of this project is to examine whether non-invasive brain stimulation, specifically transcranial direct current stimulation, can improve allocentric navigation in cognitively intact older adults and those who have been diagnosed with mild cognitive impairment (MCI) – a clinical precursor to Alzheimer’s type dementia.

Specific Aims/Hypotheses:

Specific Aim 1: Examine the effects of high definition tDCS (HD-tDCS) on both allocentric and egocentric memory test performance. We predict that participants will perform more accurately following active HD-tDCS when compared to sham HD-tDCS.

Specific Aim 2: Examine the neurophysiologic response to HD-tDCS using fMRI. We predict that active HD-tDCS will increase BOLD signal in a behaviorally meaningful way regardless of diagnostic group (i.e., healthy control vs. MCI). Critical questions about the restorative vs. compensatory effects of tDCS in those with MCI will be examined by contrasting BOLD signal change between the groups

Methodology

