constructed a mixed ANOVA model to test the influence of the aforementioned variables. Second-level maps were initially thresholded at whole-brain $p < .01$ to $.001$, uncorrected (extent threshold, $k = 10$). In addition to whole brain analysis, we also created a mask from activations seen in the whole brain analysis of task main effects (voxel-wise FWE $p < .05$) for use in group analyses of session effects. Specific regions of interests (ROIs) were also utilized, selected based on prior work (Hampstead et al., 2014) in regards to spatial navigation and derived from the Anatomical Automatic Labeling software (Tzourio-Mazoyer et al, 2002). These ROIs included hippocampus, superior parietal lobule, and caudate (all small volume corrected at voxel-wise FWE $p < .05$). Beta values of surviving brain activations were extracted and analyzed with ANOVA with significance threshold set at $p < .05$.

Resting state analysis

Resting state functional connectivity was first examined using a region of interest (ROI) "seed" at the stimulation site, right superior parietal lobule (rSPL), using a 10 mm radius spheres centered at MNI: (24, -60, 60). Pearson product-moment correlation coefficients were calculated between the average BOLD time course in the seed region and all other voxels in the brain. Each correlation resulted in a 3D correlation coefficient image (r-image). R-images were then transformed to z scores using a Fisher r to z transformation. Z score images from the individual functional connectivity analyses were entered into second-level random effects analyses (factorial ANOVA and t-tests) implemented in SPM8.

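### The active-only HC–MCI contrast does not measure a group difference in tDCS-related change, and no group-by-stimulation test is named

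*Combined protocol and SAP*

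**What the plan says.** Specific Aim 2 says that the restorative-versus-compensatory questions "will be examined by contrasting BOLD signal change between the groups". It also predicts that "active HD-tDCS will increase BOLD signal in a behaviorally meaningful way regardless of diagnostic group".

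Statistical Design plans three things that bear on this:

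- Within HC and MCI separately, "we will use the active > sham contrast to identify regions that differ as a result of HD-tDCS".
- Two exploratory between-group contrasts. The first, HC sham against MCI sham, maps disease-related differences. The second is "HC active > MCI active – which will examine whether the tDCS-related changes are greater in one group than the other". The two are to be read jointly to decide between restoration and compensation.
- Under Task analysis, a mixed ANOVA whose stated purpose is "To evaluate activations associated with task, session, and group effects". A mask from the task main effects is made "for use in group analyses of session effects". No interaction is written out. The Resting state analysis mentions a factorial ANOVA and t-tests without listing factors.

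Study Procedures describes a two-period crossover within each diagnostic group, in which the first sequence will "receive active HD-tDCS during session 1 and then sham HD-tDCS during session 2" and the second has the reverse order. Enrollment is up to 60 with no HC/MCI split, and eligible participants who cannot have MRI "will complete only the stimulation and behavioral portions of the study", so the imaging sample may be smaller.

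**The concern.** The second contrast compares two groups in one condition. A difference in change needs both conditions in both groups. If the MCI group already activates less under sham, that deficit enters the active comparison in full, and the plan's wording would report it as a difference in response to tDCS. This is the outcome to expect if Aim 2's own prediction is right and both groups gain equally. The error also runs the other way: if stimulation closes the gap in MCI, the active contrast tends to zero although the groups responded very differently.

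What is at stake is the restoration/compensation conclusion. Without a named interaction it would rest on setting suprathreshold maps beside subthreshold ones, which is not a test of the difference between groups.

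**Working it through.** **1. Identity.** Let G be the sham gap (HC sham − MCI sham) and D the difference in tDCS effects, (HC active − HC sham) − (MCI active − MCI sham). Then

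HC active − MCI active = G + D.

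This is exact. Example in SD units: HC sham 0.8, MCI sham 0, both groups gain 0.5. Active means are 1.3 and 0.5; the contrast is 0.8 although D = 0.5 − 0.5 = 0. If instead MCI gains 0.8 and HC gains 0, the contrast is 0.8 − 0.8 = 0 although D = −0.8.

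**2. Inputs.** The plan gives no power calculation to reproduce. From the documents: up to 60 enrolled; map thresholds .01 to .001 uncorrected; .05 for ANOVA on extracted betas. Assumed: 20 or 30 scanned per group, single-session SD 1, active–sham correlation ρ = 0.5, sham gap 0.3 to 0.8 SD.

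**3. Active-only contrast read alone, with zero or equal tDCS effects (D = 0).** Two-sample t test, noncentrality G × √(n/2), df = 2n − 2:

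| Gap, n per group | Noncentrality | One-sided .05/.01/.001 | Two-sided .05 |
|---|---|---|---|
| 0.8, 30 | 0.8 × 3.873 = 3.10 | 92/76/45% | 86% |
| 0.5, 30 | 0.5 × 3.873 = 1.94 | 61/33/11% | 48% |
| 0.3, 30 | 0.3 × 3.873 = 1.16 | 31/12/2% | 21% |
| 0.8, 20 | 0.8 × 3.162 = 2.53 | 80/55/24% | 69% |

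**4. Planned maps read jointly.** The plan states no decision rule, so two were simulated (n = 30, ρ = 0.5, one-sided .05/.01/.001). The three-map restoration pattern is: sham gap present, active gap absent, MCI active > sham present (40,000 runs). The four-map pattern also requires no HC active > sham effect (20,000 runs).

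| Truth | Three-map | Four-map |
|---|---|---|
| Full restoration of a 0.8 SD gap in MCI | 87/74/41% | 84/73/40% |
| No tDCS effect, gap 0.8 | 1.1/0.5/0.1% | not run |
| No tDCS effect, gap 0.5 | 2.6/0.6/<0.1% | not run |
| Equal 0.5 SD effect, gap 0.8 | 5.5/11/10% | 2.4/8.1/8.7% |
| Equal 0.5 SD effect, gap 0.5 | 16/14/4.4% | 6.5/9.5/4.0% |

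In the last two rows the gap does not change, so any restoration pattern is false. For gap 0.8 at .01, the three-map rate is 12% with ρ = 0.3 and 9.4% with ρ = 0.7.

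The within-group maps alone also mislead. If each has power p, exactly one is positive with probability 2p(1 − p). With an equal 0.5 SD effect this is 26/47/41%. At .01 it is 35%, 47% and 6% for equal effects of 0.3, 0.5 and 0.8 SD.

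**5. Interaction.** The SD of active − sham is √(2(1 − ρ)) = √(2 × 0.5) = 1, so full restoration of a 0.8 SD gap gives d = 0.8/1 = 0.8. G cancels, so with D = 0 the rate is 5/1/0.1% whatever the gap (simulated .050/.010/.001). Power for full restoration is 92/76/45% with 30 per group and 80/55/24% with 20.

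**6. Session factor.** Study Procedures numbers the sessions by visit, and stimulation order is randomized. If the ANOVA factor follows that usage, each level mixes active and sham scans, and group × session is a group × visit term. If the factor means active/sham, group × session is the test needed. The text does not say which.

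**The case against.** The strongest reply is that the plan comes close to the right test. Aim 2 names the right target, the mixed ANOVA holds group and session factors, and active/sham is a natural reading of session when each participant has one of each. This stands in part: the design and data can answer the question, and the visit reading is a possibility, not a demonstrated error. But no section writes out the interaction or ties it to this question.

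Second, the large rates in step 3 apply only if the active contrast is read alone, and the plan reads it with other maps. Also true. The joint reading usually detects real restoration and seldom misleads when tDCS does nothing. Requiring the HC map to be silent lowers the false pattern further; at .05 with a 0.8 SD gap it falls below the interaction's 5%. At the plan's map thresholds it stays well above the interaction's 1% and 0.1%. The sentence describing the second contrast also gives that contrast alone the meaning of differential change.

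Third, the interaction rates are per voxel. An interaction map at uncorrected thresholds with a 10-voxel extent would not have a known brain-wide error rate either, and the interaction alone does not separate restoration from compensation. Rates for corrected ROI tests and for a compensation scenario were not computed. One-sided .05 matches no test the plan states explicitly; the two-sided column fits the ANOVA on betas better. These points limit how the figures should be used, but not the identity.

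Finally, the analysis is labelled exploratory and additional analyses are allowed. That limits the consequence. It does not make the description of the contrast correct.

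**Conclusion.** The concern holds. The misdescription of the second contrast follows from algebra and needs no assumption, and the plan names no group-by-stimulation test. The rates are illustrative because every gap, effect, SD, correlation and group size behind them is assumed. The step 3 rates are a read-alone worst case; the joint-reading rates in step 4 better represent the plan as a whole.

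This should be fixed, but its reach is limited to the exploratory between-group part of Aim 2. The behavioral analysis and the within-group active > sham contrasts are not affected.

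**What to change.** Name the group × stimulation interaction as the test of differential response: each scanned participant's active-minus-sham image, HC against MCI, in both directions, adjusted for stimulation order. State that the ANOVA factor is stimulation (active/sham), with visit order as a separate term.

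Keep HC sham against MCI sham as the disease map. Infer restoration or compensation from where the interaction lies and its direction relative to that map, together with the within-group maps. HC active against MCI active can stay as a description of the residual gap under stimulation.

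The cost is SAP wording and one second-level contrast on images already planned. The claim becomes harder to establish: with 30 per group, a 0.5 SD difference in change has only 33% power at .01 and 11% at .001. In simulation (20,000 runs, 0.3 SD visit effect), adjusting for order left full-restoration power at 75% at .01 and 45% at .001, a loss of about one point at most, with null rates of .049/.010/.001.
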